The POWER data set also shows significant correlations between improvement in weight status and improvement in laboratory values (ALT: $r=0.46$, $p<0.0001$; non-HDL: $r=0.27$, $p=0.0022$; HgA1c: $r=0.27$, $p=0.0009$; triglycerides: $r=0.22$, $p=0.02$) (Figures 2 and 3). A large percentage of patients with abnormal labs at baseline that achieved at least a 10 point improvement in weight status (i.e. percent of 95th percentile) at approximately 6 months also achieved normalized labs (alt: 57%; triglycerides: 46%; HgA1c: 62%; non-HDL: 43%).

Cincinnati Children's Hospital Medical Center (CCHMC) and Helen DeVos Children's Hospital (HDVCH) will be the two PWM programs participating in this trial and these sites see approximately 929 and 564 new patients each year, respectively. CCHMC began enrolling patients into POWER in May, 2014 with HDVCH following in June, 2014. The demographics for adolescents with severe obesity for these two sites are very similar to the POWER population with the exception of a lower percentage of

Hispanic ethnicity (7%) and a higher percentage of Black race (31%). For these two sites, the median [IQR] number of visits by 6 months is 3 [3, 7] and the median [IQR] change in percent of the 95th percentile for BMI at 6 months is -1.7 [-4, 3] with only 6% achieving an improvement of 10 percentage points in the weight status measurement at 6 months. Significant correlations between improvement in weight status and improvement in laboratory values were also seen for patients from these two sites (ALT: $r=0.36$, $p=0.02$; HbA1c: $r=0.31$, $p=0.048$; triglycerides: $r=0.34$, $p=0.03$). Testing the feasibility and acceptability of the BPE in these two sites that are representative of the entire POWER population will provide the needed data, including estimates of treatment effects, to design a fully powered multi-site clinical trial to evaluate the efficacy of the BPE as an enhancement for existing multi-component PWM programs.

Rationale for the Study

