Hypothesis 3.1. Participants in the *Intervention* group will have a greater rate of participation in the standard-of-care PWM program as measured by percent of scheduled clinic visits and group sessions (if offered) attended over the 6-month treatment period, compared to those assigned to the *Control* group (N=20)

Hypothesis 3.2. Participants in the *Intervention* group will have a greater retention rate (percent of participants that complete the 6-month treatment period) than those in the *Control* group.

Secondary Aim 4 Test whether the *Intervention* group has better health outcomes when compared to the *Control* group after the 6-month treatment period. Health outcomes to be measured at baseline, 3-month, and 6-month assessment visits will include: 1) Weight status (BMI metric: percent of the 95th percentile); 2) Body composition (% body fat, skeletal muscle mass; fat-free mass); and 3) Blood pressure. Laboratory measures (HbA1c, ALT, non-HDL, TG, fasting glucose) will be obtained at baseline and 6-months.

Hypothesis 4. The *Intervention* group will have better health outcomes than the *Control* group.

Expected outcomes and impact: If the results of this pilot pragmatic study show that the BPE is feasible, acceptable and potentially effective, then we will have the information needed to design a fully-powered multi-site clinical trial to evaluate the efficacy of the BPE as an enhancement for existing multi-component PWM programs. If it is found that the BPE is efficacious, this evidence-based approach can then be widely implemented in order to improve the treatment of adolescents with severe obesity.

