8. DATA ANALYSIS

8.1. Study Endpoints

Demographic and clinical characteristics will be summarized overall and within each center using frequency and percent for categorical data and median and interquartile range for the continuous measurements. For each aim below, the two-sided 95% confidence intervals will be calculated using the Score Confidence Interval.³⁴ All comparisons between the intervention and control groups will be tested at the two-sided, 5% level of significance.

Aim 1: For patients in the intervention group only, percentages and two-sided 95% confidence intervals will be presented for the each of the components of the “Bundle of Program enhancements (BPE)”: a) percent of participants attending the program orientation; b) percent of participants completing each of the mental health questionnaires; 3) percent of participants completing the “readiness to change” clinical assessment; 4) percentage of participants that complete scheduling of interactive encounters (FIE) between clinic visits for 1st month of treatment; and 5) Percent of participants that complete scheduling of FIE between clinical visits for each of months 2-6 of treatment. Each confidence interval will be examined to determine if the hypothesized value of 80% is contained within the interval.

Aim 2: For patients in the intervention group only, the percentages and two-sided 95% confidence intervals will be calculated for the intervention group only for the percent of patients that complete at least 26 contact hours during the 6-month treatment period. The confidence interval will be examined to determine if the hypothesized value of 70% is contained within the interval. In addition, the mean and 95% confidence interval will be presented for the percent of FIE completed by each patient and also for the total number of contact hours completed by each patient. These measures will also be provided for the subset of patients in the intervention group that are identified with mental health problems and descriptively compared to the subset of patients in the intervention group without mental health problems.

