Aim 3: The rate of participation in on-site scheduled visits (i.e. clinic visits, group sessions) will be calculated for each patient in both the intervention group and the control group as the percentage of all scheduled visits during the 6-month period that was attended by the patient. These percentages will be compared between groups using the mixed effects model with treatment as a factor and site as a random effect. Additional covariates in the model may include baseline weight status as measured by percent of the 95th percentile, sex, race, ethnicity, socioeconomic status, and distance from clinic site. To the extent possible, interactions of covariates with treatment group will be examined and discussed if significant at $p<0.10$ level of significance.

Transformations will be used (e.g. arcsin square root, log, rank) if needed to satisfy the assumptions of the model. The percentage of patients that complete the 6-month program will be analyzed using the same approach discussed above. In addition to doing hypothesis testing, treatment differences (unadjusted and also adjusted for covariates) and 95% confidence intervals will be presented.

Aim 4: Health outcomes measured by weight status, body composition, and blood pressure will be compared between the intervention and control groups using the repeated measures mixed effects analysis with center as a random effect. The outcome metric for weight status in the proposed study will be the change in percent of the 95th percentile for BMI (based on age and sex).

For each outcome, change from baseline will be calculated and included as the dependent variable. Terms in the model will include treatment, month (i.e. 3, 6 month) and the interaction of treatment by month. If the interaction is not significant at the two-sided $p<0.10$ level, it will be removed from the model. Appropriate contrasts will be used to compare the treatment groups at 3 months and at 6 months. Covariates in the model may be the same as those listed in Aim 3. The respective baseline measure may also be included as a covariate in the model for each health outcome. Laboratory measures will be measured at baseline and at 6 months of treatment. The mixed effects model using change in laboratory measure as the dependent variable and treatment as independent variable and center as random effect will be used. Covariates may include those listed for Aim 3 and the respective baseline laboratory measure.

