8.2. Sample Size Calculation

Sixty subjects will be enrolled in this study across the two sites with 40 subjects randomized to the Intervention group and 20 subjects to the Control group. This is a pilot study and therefore confirmatory hypothesis testing will not be done. Therefore, formal power calculations were not done. Table 2 shows the width of the two-sided 95% confidence intervals for various percentages and sample sizes. Table 3 provides the treatment effects that are detectable with various sample sizes.

Table 2. Sample Size and 95% Confidence Intervals for an Observed Percentage for Study Aims 1 and 2

Observed Percentage	Sample Size			
	N=40		N=30	
	Lower 95% CL	Upper 95% CL	Lower 95% CL	Upper 95% CL
50%	35%	65%	33%	67%
65%	49%	78%	47%	79%
80%	65%	89%	63%	90%
95%	83%	99%	81%	99%

Table 3. Sample Size and Treatment Effect

Sample size Intervention/Control	Detectable Treatment Effect					
	80% Power		70% Power		50% Power	
	p<0.05	p<0.10	p<0.05	p<0.10	p<0.05	p<0.10
40/20	0.8	0.7	0.7	0.6	0.5	0.5
30/15	0.9	0.8	0.8	0.7	0.6	0.5

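### Aim 4 drops a non-significant treatment-by-month term, so the planned 6-month comparison can become a pooled 3- and 6-month effect

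*Combined protocol and SAP*

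**What the plan says.** Section 8.1, Aim 4, sets up a repeated-measures mixed model for weight status, body composition and blood pressure. On the response: "For each outcome, change from baseline will be calculated and included as the dependent variable". On the model: "Terms in the model will include treatment, month (i.e. 3, 6 month) and the interaction of treatment by month". If the interaction does not reach two-sided p<0.10, "it will be removed from the model. Appropriate contrasts will be used to compare the treatment groups at 3 months and at 6 months". The contrasts are not restricted to the case where the interaction stays in.

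Section 3, Secondary Aim 4, places the comparison with the control "group after the 6-month treatment period. Health outcomes to be measured at baseline", 3 months and 6 months. Section 8.1 also states: "All comparisons between the intervention and control groups will be tested at the two-sided, 5% level of significance".

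Laboratory outcomes follow a different schedule: "Laboratory measures will be measured at baseline and at 6 months of treatment". They have no month term, so the rule does not touch them.

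**The concern.** Removing the interaction forces the treatment effect to be equal at both visits. A 6-month contrast can still be requested from the reduced model, but it returns the same value as the 3-month contrast. A non-significant pre-test therefore changes the quantity being estimated, and the final confidence interval takes no account of that choice.

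The pooled value understates the 6-month effect if the effect grows between visits, overstates it if the effect wanes, and is right only if the effect is constant. The documents give no 3-month effect and no between-arm effect, so the direction cannot be predicted.

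The rule runs separately for six outcomes: the BMI metric, three body-composition measures, and systolic and diastolic pressure. Some could end with a true 6-month contrast and others with an average, under the same label.

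What is at stake is mainly the estimate and its interval. The preliminary-studies text in Section 2 wants data from this pilot, "including estimates of treatment effects, to design a fully powered multi-site clinical trial". A mislabelled average with too narrow an interval could mis-size that trial in either direction.

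**Working it through.** **Inputs from the documents.** 40 intervention and 20 control; interaction kept only if two-sided p<0.10; group comparisons at two-sided 0.05; Table 3 detectable effect of 0.8 for 40/20 at 80% power.

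**Assumptions not in the documents.** Complete data; no site or covariate effects; correlation ρ of 0.5 or 0.7 between the 3- and 6-month changes; equal SDs at both visits unless stated; the true effects shown below. Effects are in units of the 6-month SD.

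**1. The plan's own figure.** The SE of a single-visit contrast is √(1/40 + 1/20) = 0.274 SD. With 58 df the detectable effect at 80% power is about (2.002 + 0.848) × 0.274 = 0.78, which rounds to Table 3's 0.8. All 12 cells of Table 3 reproduce in this way. Table 3 states no unit; the match is why it is read here as SD units.

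**2. Algebra of the reduced model.** Let D3 and D6 be the arm differences at the two visits, V3 and V6 the variances of the changes, and C their covariance. Without the interaction, the one treatment coefficient is

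w·D3 + (1 − w)·D6, with w = (V6 − C)/(V3 + V6 − 2C).

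With equal variances w = 1/2. In one fitted example the full model gave 0.396 at 3 months and 0.531 at 6 months (interaction p = 0.57); the reduced model gave 0.463 at both.

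**3. Strength of the pre-test.** SE(D6 − D3) = 0.274 × √(2(1 − ρ)), which is 0.274 at ρ = 0.5 and 0.212 at ρ = 0.7. For 80% power at two-sided 0.10 the effects must differ by about (1.672 + 0.848) × SE = 0.69 or 0.53 SD. At 30/15 the figures are 0.80 and 0.62 SD.

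**4. Simulation of the two-step rule at 40/20** (40,000 trials per scenario, estimated covariance, t with 58 df). Entries are ρ = 0.5 / ρ = 0.7.

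| True effect, 3 then 6 months | Term dropped | Mean 6-month estimate if dropped | Mean over all trials | 95% CI coverage |
|---|---|---|---|---|
| 0.4, 0.8 | 58% / 41% | 0.60 / 0.61 | 0.74 / 0.76 | 90% / 92% |
| 0.25, 0.5 | 77% / 68% | about 0.38 | 0.44 / 0.45 | 92% / 92% |
| 0.8, 0.4 | 58% / 41% | about 0.60 | 0.46 / 0.44 | 90% / 92% |
| 0.8, 0.8 | 90% / 90% | 0.80 | 0.80 | 94% / 94% |

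With the term always kept, the 6-month contrast is unbiased with coverage of about 95% throughout. With 0.4 SD at 3 months and none at 6, the 6-month comparison is significant in 10% / 8% of trials, against 5% with the term kept.

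**5. Unequal SDs, as an illustration.** Let the 3-month SD be 0.75 of the 6-month SD, so V3 = 0.5625 and V6 = 1.
- At ρ = 0.5, C = 0.375 and w = 0.625/0.8125 = 0.77. At ρ = 0.7, C = 0.525 and w = 0.475/0.5125 = 0.93. The pooled value is then mostly a 3-month effect.
- With unstructured covariance, coverage is 80% / 82% for 0.4 to 0.8, and 86% / 84% for 0.25 to 0.5.
- With a common-variance structure, coverage over the same cases is 85 to 89%, and about 92% even when the term is kept.

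**The case against.** **A kinder reading.** The contrasts could be meant only for the case where the interaction stays, with one overall effect reported otherwise. Nothing would then be mislabelled. The text does not say so, however, and on that reading a dropped term leaves no 6-month estimate for that outcome. The same repair is needed.

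**The target time point.** Section 3 lists 3-month assessments, and Section 8.1 plans contrasts at both visits. Treating 6 months as the main contrast is a reading of Section 3, not a stated hierarchy; the sponsor should confirm it.

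**Size.** This is the strongest objection. With equal SDs, average bias in the growth and waning scenarios is about 0.04 to 0.065 SD, against an SE of 0.274. The site data in Section 2 give an interquartile range of -4 to 3 for 6-month change in the BMI metric. If normal, the SD is 7/1.349 = 5.2 points, so the bias is roughly 0.2 to 0.34 points. When the term is dropped in the 0.4 to 0.8 case, the shortfall is 0.2 × 5.2, about 1 point.

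**Milder growth favours the rule on some measures.** For 0.4 to 0.5 SD, its root mean squared error is 0.259 / 0.268 against 0.274 with the term kept, and coverage in the mild-growth cases is 92 to 94%. For 0.4 to 0.8 at ρ = 0.5 it is worse: 0.300 against 0.275. This stands: the rule buys precision when the effects are nearly equal. But the pre-test cannot establish that they are.

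**Unequal SDs.** The 80 to 86% coverage depends on an assumed SD ratio and on a covariance structure that Section 8.1 does not name. It is neither a forecast nor a bound: a ratio of 0.7 gives 76 to 84% for the 0.4 to 0.8 case.

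**Pilot status.** Section 8.2 says: "This is a pilot study and therefore confirmatory hypothesis testing will not be done". The 8 to 10% rejection rate therefore matters less than the estimate and its interval.

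**Conclusion.** The concern holds. That the reduced model contains no separate 6-month effect is algebra and needs no assumption. How much this matters depends on how the effect changes between visits, which the documents do not tell us. Under the equal-SD assumptions, a doubling of the effect means a loss of 3 to 5 points of coverage and an average estimate of 0.89 to 0.95 of the truth; a halving gives 1.11 to 1.16 times the truth. Unequal SDs can make it worse, and a constant effect brings no bias.

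This is a worthwhile correction to a secondary pilot aim, not a threat to the study. It is worth making because estimation is what Aim 4 is for, and the change is cheap.

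**What to change.** Delete the removal rule and replace it, for all six repeated outcomes, with text such as: *Treatment, month and treatment-by-month will be retained whatever the interaction p-value, with an unstructured covariance for the two visits. The 6-month contrast is the Aim 4 estimate; the 3-month contrast is supportive. The average effect over both months may be reported as supplementary, labelled as such. The interaction will be reported descriptively.*

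The covariance clause is a separate choice, but a useful one: if the SDs differ and a common variance is imposed, keeping the interaction alone leaves coverage at about 92%.

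The cost is one SAP sentence and some precision if the effect really is constant:
- With equal SDs, the 6-month SE exceeds the pooled SE by a factor of 1/√((1 + ρ)/2), which is 1.15 at ρ = 0.5 and 1.08 at ρ = 0.7. Power at 0.8 SD is about 82%, against 87 to 90% under the removal rule.
- With a 3-month SD of 0.75 of the 6-month SD, the SE is 34 to 39% larger, and power is 82% against 94 to 95%.

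The 82% is in line with Table 3's 0.8 at 80% power, so nothing is lost against the stated design. The supplementary average keeps the extra precision available under its correct name.

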8.2. Sample Size Calculation

Sixty subjects will be enrolled in this study across the two sites with 40 subjects randomized to the Intervention group and 20 subjects to the Control group. This is a pilot study and therefore confirmatory hypothesis testing will not be done. Therefore, formal power calculations were not done. Table 2 shows the width of the two-sided 95% confidence intervals for various percentages and sample sizes. Table 3 provides the treatment effects that are detectable with various sample sizes.

Table 2. Sample Size and 95% Confidence Intervals for an Observed Percentage for Study Aims 1 and 2

Observed Percentage	Sample Size			
	N=40		N=30	
	Lower 95% CL	Upper 95% CL	Lower 95% CL	Upper 95% CL
50%	35%	65%	33%	67%
65%	49%	78%	47%	79%
80%	65%	89%	63%	90%
95%	83%	99%	81%	99%

Table 3. Sample Size and Treatment Effect

Sample size Intervention/Control	Detectable Treatment Effect					
	80% Power		70% Power		50% Power	
	p<0.05	p<0.10	p<0.05	p<0.10	p<0.05	p<0.10
40/20	0.8	0.7	0.7	0.6	0.5	0.5
30/15	0.9	0.8	0.8	0.7	0.6	0.5

9. RISKS AND BENEFITS

9.1. Potential Benefits

There is potential for direct benefit for participating in this study. The intervention may help participants to lose weight, which has well documented emotional and physical health benefits. In addition, the information learned from this research study may benefit other patients in the future.

9.2. Potential Risks

The potential risk to patients include an individual's frustration with efforts at weight loss. There is also a potential loss of confidentiality, though study staff will work

9.3. Risk/Benefit Analysis

The proposed study has minimal risks associated with it, which are reasonable in relation to the knowledge that will be gained and used to create interventional programs in this high-risk population.

10. ADVERSE EVENTS

Events that are unexpected and considered to be related or possibly related to the study procedures as well as breaches of confidentiality, and protocol violations must be reported to the site PI and the site's IRB as soon as possible. The site is responsible for

informing the PI at CCHMC of the adverse event in a prompt and timely manner. The IRB at CCHMC will be notified of the event in a prompt manner after discovery of the event.

11. DATA SAFETY AND MONITORING PLAN

For the proposed pilot study, participants randomly assigned to the *Intervention* or *Control* group will be participating in a multi-component pediatric weight management (PWM) program for a 6-month treatment period. The PWM program for this study will be offered at two sites: Cincinnati Children's Hospital Medical Center (CCHMC), Cincinnati, OH and Helen DeVos Children's Hospital (HDVCH), Grand Rapids, MI. [name] at CCHMC and [name] at HDVCH, both serving as Co-Investigators for the proposed study, will be responsible for the oversight of the clinical management of study participants, their data collection, and address any medical issues that arise.

In addition as a requirement of all NIH-sponsored clinical trials, a Data and Safety Monitoring Board (DSMB) will be established to 1) evaluate all physiological and psychological data obtained for indications of adverse reactions; 2) investigate potential adverse events reported by the participants and/or clinical staff of the proposed study; and 3) evaluate the potential impact of these adverse events on the participants' health status and their continuation in the proposed study. The DSMB, an independent group of experts from Cincinnati Children's Hospital Medical Center (CCHMC) and the Connecticut Children's Medical Center, will be reviewing the data from this research throughout the study at both participating sites (CCHMC and Helen DeVos Children's Hospital (HDVCH), Grand Rapids, MI. The DSMB will be comprised of a physician, psychologist and biostatistician. The DSMB will meet via conference call at 3 months into the study and every 6 months thereafter, or more often as deemed necessary by the occurrence of adverse events. The "GoToMeeting" platform will be used in order to review documents during these conference calls. During the program orientation session for participants assigned to the *Intervention* group, and during the 6-month treatment period for the Intervention and Control groups of the proposed study, participants will be screened for adverse events by members of the multi-disciplinary clinical team when seen for clinic visits as part of the PWM program at each participating site, and during follow-up interactive encounters for participants in the *Intervention* group. Any adverse event will be appropriately documented and reported to the Principal Investigator, [name], RD, LD who will in turn forward all reports to the DSMB as well as the respective Institutional Review Board for CCHMC and HDVCH.

All recommendations by the DSMB will be communicated to the Principal Investigator, [name], RD, LD who will then take appropriate action as indicated. The DSMB will operate independently of the study investigators. The investigator will keep participants informed about any new information from this or other studies that may

affect the health, welfare, or their willingness to remain in the study. The individuals listed below have agreed to be members of the DSMB.

[name], MD

Associate Professor of Pediatrics, Division of Gastroenterology, Hepatology and Nutrition

Cincinnati Children's Hospital Medical Center

